Recruitment and screening	12
Data collection and grouping	12
Dataset	14
Case registration forms	14
Sample size calculation	15
Statistical analysis.....	15
Primary outcome	16
Secondary outcomes.....	16
Study organization and management	17
Study steering committee	17
National coordinators	17
Local coordinators.....	18
Investigator training.....	18
Data management and ownership	19
Publication plan	20
References	21

Summary

Short Title	LASOS-Peds
Methods	Prospective, international, multicenter observational study.
Centers	Hospitals performing pediatric surgery in participating Latin American countries.
Objectives	To assess the incidence of hospital postoperative complications in pediatric surgical patients < 18-years-old in Latin America.
Participants	10,000.
Inclusion criteria	All consecutive pediatric patients under the age of 18 years who were admitted to participating hospitals undergoing elective and nonelective surgery.
Exclusion criteria	Obstetrics.
Primary Outcome	The primary outcome is in-hospital postoperative complications up to 30 days after surgery.
Follow-up	Until hospital discharge, or a maximum of 30 days.

Background

Surgery is a cost-effective public health intervention. However, there are significant disparities in access to and in the safety of surgical and anesthesia services in low- and middle-income countries compared to high-income countries. (1) Additionally, there is a significant burden of surgical disease in the pediatric surgical population with a significant unmet need. (2,3) In Africa, children represent a significant proportion of the population, with approximately 50% of the population aged <19 years; moreover, this proportion is very similar in Latin America. (4)

Postoperative complications are an important determinant of surgical morbidity and mortality. Limited data from Africa and Latin America suggest that risk factors, incidence, and outcomes associated with pediatric surgical complications differ in high-income countries. In the South African Pediatric Surgical Outcomes Study (SAPSOS), patients in this middle-income country (5) had twice the incidence of complications (6-8), and the types of complications differed from those in high-income countries, with a predominance of infectious complications. Furthermore, risk factors for complications (including ASA physical status, urgent surgery, surgery severity, and infectious indication for surgery) were different from those in high-income countries, wherein the risk factors include post-conceptual age, ASA physical status > 3, history of cardiovascular disease, and cardiovascular, neurological, or orthopedic surgical procedures. (9) Postoperative mortality was observed to be ten times higher in

South Africa than in a prospective study in high-income countries. (10) Furthermore, a prospective study of pediatric perioperative mortality in 24 Kenyan hospitals demonstrated a 7-day postoperative mortality of 1.7% (11), which is 17 times higher than that reported in high-income countries.

The African Surgical Outcomes Study (ASOS) described surgical outcomes in African adult patients. (12) Specifically, patients had a lower risk profile and fewer complications than those in high-income countries. However, postoperative mortality was twice the global average. A similar study is being performed in Latin America (LASOS), which also includes adults.

It is necessary to determine the importance of complications in pediatric surgical patients in Latin America, as well as the risk factors and types of complications that are experienced by these patients, due to the fact that data on this population are scarce. Consequently, we will be able to target appropriate interventions and funding to improve surgical outcomes for children in Latin America.

Study objectives

Primary objective

To determine the incidence of in-hospital postoperative complications up to 30 days after surgery in Latin American pediatric surgical patients (under 18-years-old).

Secondary objectives

In pediatric surgical patients under 18 years of age in Latin America, we aim to:

1. determine the perioperative in-hospital mortality rate up to 30 days after surgery;
2. determine the incidence of severe intraoperative adverse events;
3. determine the association between preoperative, intraoperative, and infrastructural factors and postoperative complications and death.

Methods

Study design

14-day Latin American international multicenter prospective cohort study of pediatric patients (<18 years) undergoing surgery.

Inclusion criteria

All of the consecutive patients under 18-years-old who were admitted to participating hospitals during the study period and who underwent elective and nonelective surgeries will be included in the study. This analysis will include outpatient surgeries and surgical procedures outside of operating rooms requiring local or general anesthesia. Recruitment will occur for fourteen days, starting on the date chosen by each participating hospital within the study cohort period (to be determined).

Exclusion criteria

1. patients undergoing radiological or other procedures that do not require general anesthesia or in which general anesthesia is performed but no procedure is performed (e.g., general anesthesia during MRI);
2. patients undergoing obstetric surgery.

Hospitals

Our goal is to recruit as many Latin American hospitals as possible. Each hospital will receive an individual report that compares its dataset with that of the overall national cohort.

Ethics in research and informed consent

Research ethics and regulatory approvals will be sought before the initiation of the study in each location by using national research legislation/guidelines for that country.

National leaders will ensure that the necessary ethical and regulatory approvals are obtained for participating hospitals in their country. Hospitals can only record data if there is ethical approval or an equivalent waiver.

This study is a large-scale clinical audit; therefore, it does not pose a significant risk to the study population. In most, if not all, countries, there will be no requirement for individual patient consent, as all of the data will be anonymized and are expected to be recorded as part of routine clinical practice.

A precedent has already been set from an international perspective. In the original EuSOS study, consent was provided in 27 of the 28 participating European countries. (13) In the ASOS study (12) and the ASOS-2 trial, consent was provided in most hospitals. In African pediatric perioperative studies, written informed consent was provided by six of eight ethics committees in the SAPSOS

(5) study. Additionally, in a study in Kenya, written informed consent was provided in all 24 participating hospitals. (11) The LASOS study also obtained a consent form waiver from the coordinating center (Hospital das Clínicas HCFMUSP).

Informational signage documents will be used at participating sites to ensure that all of the patients and parents/guardians know that the hospital is participating in the study. These handover documents will be placed in critical areas of the participating hospitals, with explanations of the dates and nature of the study.

Recruitment and screening

We expect that all consecutive pediatric patients under 18 years undergoing elective and nonelective surgeries will be included in the study. Each hospital must record and submit a triage record of all of the eligible patients. Publicity through the appropriate hospital notices and signage will inform patients, their parents/guardians, and the public that the hospital is participating in the study.

Data collection and grouping

Each hospital will individually collect and record data on an electronic or paper case recording form (CRF) for each recruited patient. Paper CRFs will be stored in a locked office at each hospital, as they will include patient-identifiable data to allow for the tracking of clinical outcomes.

Data will be pseudoanonymized by generating a unique numeric code and transcribed by local investigators into a secure, password-protected electronic CRF on the REDCap platform. Each patient will be solely identified on the electronic CRF by their numerical code; thus, the study coordinating team can only trace the data back to an individual patient with contact with the local team. A participant (patient) list will be used at each hospital to match the identification codes in the database to individual patients to record clinical results and to provide any missing data points. Access to the data entry system will be protected by the username and password provided during the registration process to individual local investigators. All of the electronic data transfers between participating hospitals and the coordinating center will be encrypted by using a secure protocol (HTTPS/SSL 3.0 or higher).

When individual hospitals are unable to access the registration form over the internet, pseudoanonymous coded data can also be faxed, registered mailed, emailed, or WhatsApp messaged to the coordinating center (if necessary).

Each hospital will maintain a secure trial file, including a protocol, local investigator delegation record, ethics approval documentation, participant list, and other documentation (such as trial definitions).

A printout of the final summary of the included patients with essential variables should be produced for each hospital, along with the submission of final data for double-checking for completeness and accuracy.

Dataset

A realistic dataset will be critical to the success of the investigation, and this requirement was confirmed in the EuSOS (13), SASOS (14), and SAPSOS (5) studies, wherein almost complete data were available on the patients. Based on the SAPSOS and ASOS-Paeds study, we plan to adopt this dataset with minor changes to remove data that are deemed to be redundant to develop a simple, lean, and pragmatic dataset. We believe this simple dataset will encourage hospitals to participate.

Hospital-specific data will be collected once, including hospital level of care (primary, secondary, and tertiary), number of operating rooms, number of specialists, number and level of intensive care beds, equipment suitable for pediatric surgery and anesthesia, availability of drugs and blood products, details of hospital reimbursement status, and holidays or other local factors that affect patient flow during the study period.

Case registration forms

A CRF LASOS-Peds will be completed for each eligible patient who undergoes surgery during the cohort period. Patients will be followed up until hospital discharge. This will be censored in thirty days; specifically, patients will be followed up until discharge or for thirty days after surgery if they are still in the hospital.

Sample size calculation

We plan to recruit as many hospitals from each participating country as possible and ask them to include all eligible patients in the study. We do not have a specific sample size, and statistical models will be adapted to the event rate provided by the recruited sample to avoid inappropriate use of any logistic regression models.

Statistical analysis

The data to be collected are all collected as part of routine clinical care. Categorical variables will be described as proportions and compared by using chi-square tests. Continuous variables will be described as the mean and standard deviation if normally distributed or as the median and interquartile range if not normally distributed. The univariate analysis will test factors associated with postoperative complications, intensive care admission, and in-hospital death.

Hierarchical multilevel logistic regression models will be constructed to identify factors that are independently associated with these outcomes and to adjust for differences in confounding factors. Factors will be entered into the models based on their univariate relationship with the outcome ($p < 0.05$), biological plausibility, and low rate of missing data. Logistic regression results will be reported as adjusted odds ratios (ORs) with 95% confidence intervals. Moreover, models will be evaluated by using sensitivity analyses to explore

possible interacting factors and to examine any effect on the results. A statistical analysis plan will be written before the analysis.

Primary outcome

Postoperative complications in the hospital up to 30 days after surgery.

Secondary outcomes

1. Mortality on the day of surgery;
2. Hospital mortality up to 30 days after surgery;
3. Risk factors associated with in-hospital complications;
4. Severe intraoperative critical adverse events;
5. Level of qualification of anesthesia and surgery providers, as well as the number of specialists per pediatric population;
6. Admission to intensive care.

Study organization and management

Study steering committee

The Steering Committee will be chaired by the leading researcher. The study management team will be appointed by the Steering Committee and led by the principal investigator. This team's duties will include the following:

- administration of all project tasks;
- communication between project partners (including funders, Steering Committee members, and national and local coordinators);
- data collection and management;
- preparation of reports to project sites;
- individual study.

The Steering Committee is responsible for the scientific conduct and consistency of the project. The Steering Committee will ensure communication between the funder(s), the trial management team, and coordinators, as needed.

National coordinators

The Steering Committee will appoint national coordinators to lead the project in each country and:

- identify local coordinators at participating hospitals;
- assist in translating study paperwork, as needed;

- ensure the distribution of research manuals and other research materials;
- ensure necessary regulatory and ethical approvals are in place before recruitment;
- ensure good communication with participating sites in your country.

Local coordinators

Local coordinators at individual institutions will have the following responsibilities:

- provide leadership for study at your institution;
- ensure that all relevant regulatory and ethical approvals are in place for your institution;
- ensure proper training of all relevant personnel before data collection;
- oversee daily data collection and site recruitment, as well as follow-up on management;
- act as a guarantor of the integrity and quality of the collected data;
- ensure the timely completion of electronic CRFs;
- communicate with the national coordinator.

Investigator training

Training will be performed by using instructional videos posted on the study website. Each site must complete an online questionnaire as part of the baseline before starting data collection.

Data management and ownership

On behalf of the Steering Committee, the Academic Research Organization of Instituto do Coração, Hospital das Clínicas, Faculdade de Medicina, Universidade de São Paulo will be a data custodian. The Steering Committee will retain the right to use all of the pooled data for scientific and other purposes. The LASOS-Peds study group members will have the right to access the pooled data for research purposes, provided that the research proposal has been reviewed and deemed appropriate by the Steering Committee. The primary consideration for such decisions will be the quality and validity of any proposed analysis. Only summarized data will be presented publicly, and all of the institutions will be anonymized (except in the individualized report provided to each institution at the end of the study). Individual patient data supplied by participating centers remain the property of the respective institutions.

Publication plan

Data will be promptly edited and released. The Steering Committee will appoint a Writing Committee to write this investigation's scientific report(s). The group will be known as 'The LASOS-Peds Investigators'. It is anticipated that several secondary analyses will be performed. LASOS-Peds investigators will be given priority to conduct such analyses and encouraged to do so. Participation and authorship opportunities will be based on contributions to the primary study. Upon request, hospitals will receive an individual report that allows for the comparison of the summary data from their particular hospital with that of their national cohort. In conjunction with the principles of data preservation and sharing, the Steering Committee will consider all reasonable requests to make the dataset available in whole or in part for secondary analysis and scientific publication upon publication of the general dataset. The Steering Committee will consider scientific validity and the possible effect on the anonymity of participating hospitals before granting such requests. Where appropriate, a prior written agreement will set out the terms of such collaborations. The Steering Committee will consider proposals for secondary reviews based on the scientific quality of the proposal. Furthermore, the Steering Committee must approve the final version of all of the manuscripts before submission, whether they relate to part or all of the LASOS-Peds dataset.

References

4. 2014 World Population Data Sheet, 2014.
6. GlobalSurg C. Determinants of morbidity and mortality following emergency abdominal surgery in children in low-income and middle-income countries. *BMJ Glob Health* 2016;1(4):e000091.

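### Inclusion text and exclusion 1, read literally, classify surgery without general anesthesia in opposite ways, so the primary denominator can differ between hospitals

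*Protocol*

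**What the plan says.** Four places in the protocol bear on who is eligible.

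- **Methods, Inclusion criteria.** Consecutive patients under 18 "who underwent elective and nonelective surgeries will be included in the study", with no limit on anesthesia technique. The next sentence adds: "This analysis will include outpatient surgeries and surgical procedures outside of operating rooms requiring local or general anesthesia".
- **Methods, Exclusion criteria, item 1.** This removes "patients undergoing radiological or other procedures that do not require general anesthesia or in which general anesthesia is performed but no procedure is performed", with MRI under general anesthesia as the example. Item 2 removes obstetric surgery.
- **Summary.** The row reads "Exclusion criteria Obstetrics". Exclusion 1 does not appear there.
- **Recruitment and screening.** The population is restated as all consecutive patients under 18 having surgery, again without an anesthesia limit. Sites apply the rule themselves: "Each hospital must record and submit a triage record of all of the eligible patients".

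The primary objective is a proportion in this population: "To determine the incidence of in-hospital postoperative complications up to 30 days after surgery in Latin American pediatric surgical patients".

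**The concern.** A child who has a minor operation under local anesthesia outside the operating room is expressly admitted by the inclusion sentence. The same child has also had a procedure that did not need general anesthesia, which is what the first half of exclusion 1 removes. A coordinator who reads the criteria in order can reasonably go either way.

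The eligible set is the denominator of the primary outcome. It also underlies the secondary outcomes of mortality and intensive care admission. Secondary objective 3 relates infrastructural factors to outcome, and each hospital's data are to be compared with its national cohort. If sites treat a whole stratum of cases differently, part of any difference between hospitals could reflect the reading of the criteria and not patient outcome.

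A later analysis plan could not repair this. Under Case registration forms, a CRF is completed for each eligible patient, and the triage record also covers eligible patients. A site that follows exclusion 1 literally would have no CRF for these children and no duty to list them, so they could be neither analysed nor counted afterwards.

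**Working it through.** No stated figure depends on this point, so there is none to reproduce. The check compares the texts and then gives an illustration of size.

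**Step 1: classify each type of case under each text, read literally.**

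| Case | Inclusion criteria | Exclusion 1 | Summary |
|---|---|---|---|
| Surgery under general anesthesia | in | not removed | in |
| Surgery under local anesthesia only | in (local is named) | removed | in |
| Surgery under regional block or sedation | in (all surgery; technique not named) | removed | in |
| General anesthesia with no procedure (MRI) | not surgery | removed | not surgery |
| Obstetric surgery | in | not removed (item 2 removes it) | out |

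The second and third rows conflict. The local-anesthesia row is the clearest, because the inclusion text names that technique.

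**Step 2: look for text that settles it.** The other procedures in exclusion 1 are not defined. The MRI example illustrates the second half of the criterion (anesthesia given, nothing performed), not the first. No order of precedence is given. The protocol mentions trial definitions in each hospital's file, research manuals and training videos, but their content is not shown.

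**Step 3: illustrate the size.** The documents give neither the share of cases done without general anesthesia nor complication rates by technique. All rates and shares below are assumptions, including that local-anesthesia cases carry lower risk.

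- Complication rate with general anesthesia, p_GA: 10% to 15%
- Complication rate with local anesthesia only, p_LA: 1% to 3%
- Share of local-anesthesia cases, s: 5% to 30%
- N = 10,000, from the Summary ("Participants 10,000"); the sample size section says there is no specific target, so this is a reference value only

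Incidence with these cases counted = (1 − s)·p_GA + s·p_LA. Incidence without them = p_GA. The shift is therefore s·(p_GA − p_LA).

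- Smallest: 0.05 × (0.10 − 0.03) = 0.0035, or 0.35 points
- Example: 0.20 × (0.15 − 0.01) = 0.028, so 15.0% without and 12.2% with, a shift of 2.8 points
- Largest: 0.30 × (0.15 − 0.01) = 0.042, or 4.2 points

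For scale, the 95% half-width is 1.96·√[p(1 − p)/N]. At p = 7.3% it is 0.51 points, and at p = 14.4% it is 0.69 points. With s of 10% or more the shift exceeds the half-width in every combination; the closest is 0.70 against 0.57 points. With s = 5% it is about equal or smaller (0.35 to 0.70 against 0.58 to 0.69 points).

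Two features of this illustration overstate the contrast. It compares every site including with every site excluding, and mixed practice would move the pooled figure less. The half-width also treats patients as independent, and clustering by hospital would widen it.

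**The case against.** The strongest reply is that a consistent reading exists. The inclusion text speaks of surgery and surgical procedures. Exclusion 1 does not use the word surgical, starts from radiology and ends with MRI. Where surgery itself is excluded, in item 2, the protocol says so. On this reading exclusion 1 only marks what is not surgery, a local-anesthesia operation stays in, and the Summary needs to list only obstetrics. The restatement under Recruitment and screening fits this too.

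Much of this stands. It makes the problem an ambiguity with a plausible resolution, and the narrow reading may well be what was meant. But the text does not say it, and the literal reading is open to any site.

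Three stronger inferences are tempting and should not be drawn.

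- **That the protocol defines three different populations.** Under the narrow reading the Summary agrees with the Methods, so its omission of exclusion 1 is only one more text to align.
- **That hospitals will enrol differently.** The manuals and training may impose one rule. The documents support only that hospitals can differ.
- **That the primary result will be off by a given amount.** No rate or share by anesthesia technique is in the documents.

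It is also fair to say that the patient-level CRF is not shown, so nothing indicates that anesthesia type goes unrecorded. Reporting by anesthesia type is a matter for the analysis plan.

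**Conclusion.** The concern holds as a wording conflict in the eligibility rule. Read literally, the inclusion text and exclusion 1 put surgery under local anesthesia alone on opposite sides, and the exclusion wording also catches regional block and sedation. The reading that would reconcile them is not written down. Site-dependent enrolment is therefore possible, and cases dropped at a site could not be restored later.

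The conflict itself rests on the text alone. The range of 0.35 to 4.2 points rests wholly on assumed rates and shares and shows only that the effect could be smaller or larger than the sampling error. It is not an estimate of bias in this study.

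**What to change.** Use one rule in the Summary, the inclusion text and exclusion 1. One way that respects the inclusion sentence:

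- Confine the first half of exclusion 1 to radiological and other **non-surgical** procedures done without general anesthesia. Keep the second half for general anesthesia given with nothing performed, as in the MRI example.
- State that surgery under any anesthesia technique (general, regional, local or sedation) is eligible.
- Leave the status of radiological or diagnostic procedures that do require general anesthesia as it is. Exclusion 1 does not now remove them when a procedure is performed, and a broader rewrite that excluded diagnostic or radiological work with or without general anesthesia would create a new denominator question.
- Align the Summary row, and repeat the rule in the trial definitions and site training.

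If the sponsor intends the opposite, that local-anesthesia surgery is out, the inclusion sentence is the one to change. Either way the three texts must match.

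The cost is a one-paragraph correction, a Summary line and a training line, with no extra patients. It needs to be in place before sites enrol, because the loss cannot be made good afterwards.

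### Eligibility depends on surgery having taken place, so a child whose operation is abandoned after induction can drop out of the cohort, and out of the intraoperative-event and mortality outcomes

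*Protocol*

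**What the plan says.** Four places in the Protocol decide whether a child enters the cohort.

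- **Inclusion criteria.** Consecutive patients under 18 admitted in the study period "who underwent elective and nonelective surgeries will be included in the study". The test is that surgery took place.
- **Exclusion criteria, item 1.** The clause opens with "patients undergoing radiological or other procedures that do not require general anesthesia". It then adds a second limb, for cases "in which general anesthesia is performed but no procedure is performed (e.g., general anesthesia during MRI".
- **Recruitment and screening.** Each hospital submits a triage record, but only of eligible patients.
- **Case registration forms.** "A CRF LASOS-Peds will be completed for each eligible patient who undergoes surgery during the cohort period".

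Secondary objective 2 is to "determine the incidence of severe intraoperative adverse events". The secondary outcomes include "Mortality on the day of surgery" (item 1), in-hospital mortality to 30 days (item 2) and "Severe intraoperative critical adverse events" (item 4). Secondary objective 1 describes the mortality of interest as perioperative, not only postoperative.

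**The concern.** The period between induction of anesthesia and the start of the procedure is one in which severe events can occur. A child who has a cardiac arrest or a failed airway at induction, and whose operation is therefore called off, has had the kind of event that the study sets out to count. Under rules that ask whether surgery was done, that same event removes the child from the cohort. Entry then depends on the outcome.

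Two things make this a protocol matter. First, the loss has a known direction: leaving out children whose operation was stopped by a crisis can lower the counts of severe events and early deaths but cannot raise them. Second, it cannot be repaired at analysis. A child judged ineligible at the hospital gets no form and need not appear in the triage record, so a later analysis plan would have nothing to work with. Hospitals that read the wording differently would also count different populations, and the protocol promises each hospital a comparison with its national cohort.

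**Working it through.** **Reading the rules against one case.** Take a child anesthetized for planned surgery whose operation is abandoned before it begins.

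1. *Inclusion rule:* the child did not undergo surgery, so is not included as the rule is worded.
2. *Case form rule:* it applies to an eligible patient who undergoes surgery, so no form is completed.
3. *Triage record:* it lists eligible patients only, so the child need not be logged.
4. *Exclusion 1:* unclear. Its subject is patients undergoing radiological or other procedures, and its only example is MRI, which suggests imaging. But other procedures are not limited to non-surgical ones, the example is only an example, and the second limb turns on what was performed and not on what was planned. A site could apply it to this child.
5. *Any rule that keeps the child in:* none in the visible text.

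A child whose crisis or death comes after the procedure has started meets rules 1 and 2 and stays in. The gap is confined to the interval before the procedure begins.

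**Scale, as an illustration only.** The protocol has no figure to reproduce here. Inputs:

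- N = 10,000, from the Summary (the sample size section says that there is no specific target).
- True mortality m = 1.7%, the 7-day figure from the Kenyan cohort in the Background, and 1.7% / 17 = 0.1%, the high-income figure that the same sentence implies. Neither is a forecast for Latin America or for the day of surgery.
- k = 1, 2 or 5 deaths lost before the procedure starts. This is assumed.

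With D = N × m, observed mortality is (D − k)/(N − k), and the relative understatement is 1 − observed/m.

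| m | D | k | Observed | Understatement |
|---|---|---|---|---|
| 0.1% | 10 | 1 | 9/9,999 = 0.090% | 10% |
| 0.1% | 10 | 2 | 8/9,998 = 0.080% | 20% |
| 0.1% | 10 | 5 | 5/9,995 = 0.050% | 50% |
| 1.7% | 170 | 1 | 169/9,999 = 1.690% | 0.6% |
| 1.7% | 170 | 2 | 168/9,998 = 1.680% | 1.2% |
| 1.7% | 170 | 5 | 165/9,995 = 1.651% | 2.9% |

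For comparison, the simple binomial 95% half-width, 1.96 × √(m(1 − m)/N), is 0.062 percentage points at 0.1% and 0.253 points at 1.7%, ignoring clustering by hospital. Even k = 5 shifts the estimate by about 0.05 points, which is inside both.

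For severe intraoperative events every input must be assumed. If 0.05% to 0.2% of 10,000 cases are abandoned for an adverse event, that is 5 to 20 children. Against 300 to 500 severe events in all, the loss is between 5/500 = 1.0% and 20/300 = 6.7%.

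**The case against.** The strongest reply is that exclusion 1, read whole, concerns anesthesia for imaging and similar non-surgical care. A reader who starts at its second limb might infer that it removes every child given general anesthesia in whom no procedure follows. The documents do not support that: the opening words and the MRI example point elsewhere, and a surgical booking is not clearly covered. This part of the reply stands, and it is why the point rests mainly on the inclusion rule and the case form rule.

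A second reply is that a cohort of children who had surgery is a legitimate choice and fits a primary outcome of postoperative complications. That also stands for the primary outcome: a child with no operation does not belong in that denominator. It does not answer the point for intraoperative events and perioperative mortality, which the protocol also sets out to measure.

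Third, a reader might infer that weaker hospitals abandon more cases, so that associations with infrastructure are pulled towards no difference. Nothing in the protocol shows this. Secondary objective 3 concerns postoperative complications and death, not intraoperative events, and the secondary outcome on provider qualification and specialist numbers is descriptive.

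Fourth, not every abandoned case involves a severe event. An equipment fault could also stop an operation after induction, and leaving such a child out only trims the denominator.

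Finally, the trial definitions held at each site and the case form itself are not shown, and either could deal with abandoned cases. That possibility remains open, but the eligibility text should not depend on it.

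**Conclusion.** The gap is real but narrow. As worded, the inclusion and case form rules leave out a child whose planned operation is abandoned between induction and the start of the procedure, exclusion 1 can be read the same way, and no visible text brings the child back. When the reason is a crisis or a death, the omission depends on the outcome, and it understates severe intraoperative events, day-of-surgery mortality and in-hospital mortality.

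The direction is clear; the size is not. It depends on an abandonment rate that the protocol does not give. It is probably small in absolute terms, though the relative effect could matter if early deaths are few. The primary outcome is not shown to be biased. This is a cheap improvement to secondary outcomes, worth making before recruitment because the lost cases cannot be recovered later.

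**What to change.** 1. Limit exclusion 1 to general anesthesia given when no surgical or interventional procedure was planned, with MRI kept as the example.
2. State in the inclusion criteria and in the case form rule that a child in whom anesthesia is started for a planned eligible procedure stays in the cohort if the procedure is abandoned for any reason.
3. Add a tick box to the case form for a procedure abandoned after the start of anesthesia, with the reason.
4. Count these children in the numerators and denominators of the intraoperative-event and mortality outcomes. Both mortality outcomes are timed from surgery, so say that for these children time runs from the start of anesthesia.
5. Restrict the primary postoperative-complication analysis to children who had surgery, and report abandoned cases separately.

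The cost is a few sentences and one form item. A few children will have no surgical-severity value and will need their own category in the models, and comparability with the sister cohorts is slightly reduced. Reporting the secondary outcomes with and without the abandoned cases would show how much difference they make.
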